7.4 Adjustments for Multiple Comparisons

In general, although this post-market study has multiple primary endpoints, they are not hypothesis-driven and therefore their results will be presented descriptively with no adjustments for multiple comparisons. For comparisons between pre-market results and post-market results, however, these comparisons will account for multiple comparisons. Two comparisons between the pre-market study (DEN170004) and the post-market study are anticipated, for Primary Safety Objective #1, and components of Secondary Objective #4. A Bonferroni adjustment to the alpha-level to determine the quantile for the confidence intervals (CIs) in those analysis will be performed. Thus, confidence intervals for these comparisons will be based on 97.5% CIs rather than 95% CIs.

7.5 Demographic and Other Baseline Characteristics

Demographic and baseline characteristics will be presented for the Safety population.

Demographic characteristics including age, gender, body mass index, ethnicity, and race will be summarized using descriptive statistics and 95% CIs.

Relevant co-morbidities and surgical history will be presented as the number and percentage of subjects with each condition or procedure. Surgical history is collected separately for each side of the body and will be presented in relation to the side of the body on which the study AVF was created: Ipsilateral (same side) or Contralateral (opposite side).

Relevant demographic and baseline characteristics will be descriptively compared to the pre-market study (DEN170004). If the studies differ with respect to demographics, additional analyses or adjustments may be required for endpoint comparisons between studies.

Relevant concomitant medication use at baseline will be presented as the number and percentage of subjects taking aspirin, Plavix, Coumadin, other anti-coagulant medications, or other anti-platelet medications, as well as the indication(s) for treatment.

The time since hemodialysis (HD) started and current method of HD will be summarized descriptively.

7.6 Treatment Characteristics

Subjects may have an additional AVF access attempted if the first attempt does not lead to successful AVF creation. Summaries of AVF creation procedures will be presented for the Safety population.

Descriptive summaries will be presented for pre-procedure ultrasound vein mapping, pre- and intra-operative medication use, elapsed time for each stage of the procedure, and procedure outcomes, including the number and percentage of subjects for whom:

- access was achieved,
- the device was deployed,
- an AVF was created,
- an intra-operative percutaneous transluminal angioplasty (PTA) procedure was performed,
- AVF was patent at discharge,
- any AEs occurred, and
- the number of access attempts leading to a successful AVF creation procedure.

The summary of the intra-operative PTA procedure will include largest balloon size used, location of the PTA, and whether any complications occurred.

For subjects who did not have a fistula created, the reasons will be tabulated.

Post-procedure ultrasound measurements of artery and vein mean flow rates and diameters will be summarized descriptively. Not all measures will be available due to normal variations in subject anatomy; missing values will be ignored.

Relevant concomitant medication use during the study will be summarized at each visit for the Safety population, and will be presented as the number and percentage of subjects taking aspirin, Plavix, Coumadin, other anti-coagulant medications, or other anti-platelet medications.

7.7 Evaluation of Objectives

7.7.1 Primary Effectiveness Objective

Cumulative Patency through 12 months post AVF creation

Analysis Dataset:

Treated Analysis Set per section **Error! Reference source not found..**

Analysis Method:

Cumulative patency will be summarized for the Treated population using a Kaplan-Meier curve through at least 12 months. Analyses will include patency/survival probabilities and 95% confidence interval bands through the 12-month visit. The confidence interval will be calculated using a typical transformation of the survival function: $\log(S(t))$. Subjects not completing the study will be censored after their last available visit. A sensitivity analysis shall be performed where a cumulative incidence curve is estimated and death will be accounted for as a competing risk. The cumulative incidence curve will be descriptively compared to $1-S(t)$ where $S(t)$ is the survival function estimated by the Kaplan-Meier method.

The observed cumulative incidence estimate may be calculated using the “cmprsk” library in R, with code similar to the following:

```
cmpout1 <- cuminc(time,event)
```

The event variable is 0 if censored, 1 if an event occurs and 2 if a death occurs. Similar code in SAS is possible using the following:

```
proc lifetest;  
  time T*event(0) / failcode=1;  
run;
```

where T is the time variable, event takes a value of 1 for primary events, a value of 0 as a censored observation indicator, and all other values as competing events.

Endpoint Definition:

Cumulative patency is defined as freedom from access abandonment from time of access creation. An abandoned dialysis access is one that can no longer be used for one or two needle prescribed dialysis because it is unable to provide adequate blood flow and/or is deemed unsafe for the patient, and the associated problem cannot be corrected by any intervention either medical, endovascular or surgical. Access abandonment due to kidney transplant, for example, shall not contribute to the endpoint and date of censoring is the date their access is abandoned. For time-to-event analysis, day 0 is time of

access creation and final date is day of event or day of last follow-up. The definition of cumulative patency is derived from reporting standards by Sidawy, et al and Shenoy, et al [1,2].

Additional Analysis:

- Cumulative patency post- surgical or endovascular intervention
- The association between early occlusion and cumulative patency through 12 months will be summarized for the Treated population. Kaplan-Meier curves and associated life tables will be generated summarizing cumulative patency comparing curves for subjects who experience and do not experience early occlusions.
- The association between the number of secondary procedures required to facilitate maturation or maintain the functionality of a patent access and cumulative patency through 12 months will be summarized for the Treated population. Kaplan-Meier curves and associated life tables will be generated summarizing cumulative patency for subjects having 0, 1, 2, 3 and 4 or more secondary procedures.

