7.7.4 Secondary Objective #3

Rate of Secondary Procedures

Analysis Dataset:

Treated Analysis Set per section **Error! Reference source not found..**

Analysis Method:

Secondary procedure rate will be summarized cumulatively through 12 months as the number of procedures per person-years as well as the number and percentage of subjects having one or more procedures in the Treated population. This summary will be presented overall and by type of procedure (surgical or percutaneous). Additionally, the number of secondary procedures will be summarized categorically as the number and percentage of subjects with 0, 1, 2, 3, or 4 or more procedures.

Summaries specific to PTA/balloon maturation interventions will be provided. These summaries will be based on secondary procedures that include a PTA/balloon maturation intervention, whether performed alone or in combination with other interventions. The summaries will be presented for interventions performed post-AVF creation through 12 months. The summaries will include the number of PTA interventions performed, whether the PTA was performed in combination with other interventions, the rate of intervention in person-years, the location and average balloon size. Similar summaries will be provided for stent, embolization, and valvulotomy interventions, presented cumulatively through 12 months.

This endpoint will also be summarized by type of procedure (e.g. banding, balloon maturation, transposition/elevation/ superficialization, etc.), indication (due to stenosis, due to AE, etc.), procedure success and association with any AEs.

Endpoint Definition:

Secondary procedures are surgical or percutaneous interventions designed to mature or maintain the AVF or re-establish flow. Secondary procedures are procedures subsequent to completion of the AVF creation procedure.

Additional Analysis:

- The association between the occurrence of acute anastomotic disruption or pseudoaneurysm and the secondary procedure rate for the Treated population. The mean number of secondary procedures will be summarized cumulatively and stratified by subjects who experienced anastomotic disruption or pseudoaneurysm and those who did not.
- The association between the occurrence of early occlusions and the secondary procedure rate for the Treated population. The mean number of secondary procedures will be summarized for subjects who experienced an early occlusion and those who did not.

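### Patency curves grouped by the total number of secondary procedures received during follow-up carry immortal-time bias and cannot be read as an association

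*SAP*

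**What the plan says.** SAP 7.7.1 defines the endpoint and its clock: "Cumulative patency is defined as freedom from access abandonment from time of access creation". Day 0 is the time of "access creation and final date is day of event or day of last follow-up". An access counts as abandoned only when "the associated problem cannot be corrected by any intervention either medical, endovascular or surgical".

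Under Additional Analysis, the same section proposes to summarise the association between the number of secondary procedures and cumulative patency through 12 months. It does so with Kaplan-Meier curves and life tables in the Treated population, "summarizing cumulative patency for subjects having 0, 1, 2, 3 and 4 or more secondary procedures". Protocol 13.2.3 carries the same text. SAP 7.7.4 fixes when procedures are counted: "Secondary procedures are procedures subsequent to completion of the AVF creation procedure".

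There are two companion analyses. SAP 7.7.1 also plans patency curves "comparing curves for subjects who experience and do not experience early occlusions". SAP 7.7.4 plans this: "The mean number of secondary procedures will be summarized for subjects who experienced an early occlusion and those who did not", and a similar comparison by anastomotic disruption or pseudoaneurysm. The main summary in 7.7.4 uses a different metric, "summarized cumulatively through 12 months as the number of procedures per person-years".

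Neither document gives a landmark, a time-dependent covariate, a reset time origin or a counting window for the procedure groups. A separate bullet on patency after surgical or endovascular intervention states no method and leaves this grouping unchanged.

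**The concern.** The group label is earned during the risk time that the curve describes. To reach the 3 or 4+ group, a subject must keep an un-abandoned access long enough to receive that many procedures. An access abandoned at week 3 can hardly leave the 0 or 1 group. Abandonment ends accrual by definition, and so does dropout. The low-count groups therefore collect the early failures, and the high-count groups contain time in which failure was impossible by construction.

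The curves sit under the primary effectiveness objective, and Protocol 15.8.2 sends study reports to FDA. A reader could take them to show that repeat intervention preserves the fistula, or that fistulas left alone do badly.

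The 0 group needs particular care. Protocol Table 6 notes that balloon maturation was required in 99% of pre-market subjects and expects similar procedures after the index procedure. If that holds, the 0 group may be very small. It may consist largely of accesses abandoned, or subjects lost, before a first procedure, rather than of fistulas that needed none.

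The mean-number comparisons in SAP 7.7.4 have a related fault: a subject followed for less time has less time to accrue procedures.

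**Working it through.** **Plan's own figure.** The documents state no figure for these curves. The one computable design figure reproduces: 100 / 0.75 = 133.3, rounded up to 134. It supplies n = 134 and 25% dropout.

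**Assumptions.** Neither document gives an expected patency or procedure rate. I took 12-month patency S = 70%, 80% or 90% and a procedure rate μ between 1 and 3 per person-year. Abandonment is exponential. Procedures follow a Poisson process independent of abandonment, so there is no association by construction.

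**Closed form for the 0 group, no dropout.** Let λ = −ln S, which is 0.2231 per year for S = 0.80. Among subjects whose final count is 0:

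P(patent at 12 months) = e^−(λ+μ) / [ e^−(λ+μ) + (λ/(λ+μ))·(1 − e^−(λ+μ)) ]

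- μ = 1.5: 0.1785 / (0.1785 + 0.1064) = 62.7%
- μ = 2: 0.1083 / (0.1083 + 0.0895) = 54.7%

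The true value is 80%. For 1, 2 and 3 procedures at μ = 2, numerical integration gives 78.6%, 87.4% and 91.4%.

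**Planned curves with 25% dropout.** Simulation of 400,000 subjects, Kaplan-Meier at 12 months by final count:

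| True patency, rate per person-year | 0 | 1 | 2 | 3 | 4+ |
|---|---|---|---|---|---|
| 80%, 1.0 | 70.8 | 85.1 | 90.5 | 93.0 | 94.8 |
| 80%, 1.5 | 65 | 82 | 89 | 92 | 95 |
| 80%, 2.0 | 59.4 | 79.0 | 87.4 | 91.2 | 94.1 |
| 80%, 2.0, with 80% of procedures in first 3 months | 69.1 | 78.5 | 82.4 | 84.9 | 86.8 |
| 70%, 3.0 | 32.5 | 58.4 | 74.6 | 82.6 | 89.4 |
| 90%, 1.0 | 84.8 | 92.6 | 95.2 | 96.8 | 97.3 |

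**At n = 134, still no association.** Among simulated trials with at least 5 subjects in each group, the 3+ group beat the 0 group as follows:

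- 80%, 2 per year: 99.9% of trials, median gap 33 points
- 90%, 2 per year: 98.3%, 19 points
- 80%, 1 per year: 96.3%, 24 points
- 80%, 2 per year front-loaded: 91.6%, 16 points

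**Confounding by indication.** A shared gamma frailty was added that raises both the abandonment hazard and the procedure rate (base 80% patency, 2 per year). Patency for 0 versus 4+ procedures:

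| Frailty variance | Constant rate | Front-loaded |
|---|---|---|
| 0.5 | 75.9 vs 86.4 | 83.8 vs 75.6 |
| 1 | 82.7 vs 81.5 | 88.6 vs 69.0 |
| 2 | 88.8 vs 73.8 | 92.9 vs 61.6 |

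The slope can be positive, flat or negative.

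**Landmark, no association.** True patency from month 3 to month 12 is 0.80^0.75 = 84.6%. At 1.5 per year, the 0, 1 and 2+ groups classified at Day 90 all come out within about 0.2 points of that.

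Group sizes: 134 × (0.80 × 0.75)^(90/365) ≈ 118 still at risk. The Poisson mean by Day 90 is 1.5 × 90/365 = 0.37, so P(2+) = 1 − e^−0.37 × 1.37 ≈ 0.054, about 6 subjects. Fewer than 1 would have 3+.

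**Mean number of procedures.** At an identical 1.5 per person-year, the mean count is 1.5 × (1 − e^−h)/h, where h is the abandonment hazard plus the dropout hazard (−ln 0.75 = 0.2877).

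- Patency 80%: h = 0.5108, 1.5 × 0.4/0.5108 = 1.17
- Patency 40%: h = 1.2040, 1.5 × 0.7/1.2040 = 0.87

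The difference comes only from time at risk.

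**Early-occlusion curves.** The group is fixed by Day 7. At 80% patency, 1 − 0.80^(7/365) = 0.43% of accesses are abandoned by then, or 0.6 of 134. Patency from Day 7 is 0.80^(358/365) = 80.3% against 80.0%.

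**The case against.** The strongest reply is that this is one descriptive bullet under Additional Analysis. No test or decision rule uses it, and the overall Kaplan-Meier estimate with its competing-risk sensitivity analysis is untouched. That stands, and it limits the seriousness of the point. It does not excuse the display, whose stated purpose is to summarise an association.

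A reader might infer that the reported curves will show a strong dose-response in favour of repeat intervention. The documents do not support that. They describe procedures prompted by low outflow, stenosis, adverse events or the need to restore flow, so worse fistulas are likely to receive more of them. That works against the immortal-time effect and can reverse it.

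The 65% to 95% spread also should not be read as a forecast. A constant 1.5 per year leaves about 47 of 134 subjects with no procedure, which fits poorly with near-universal balloon maturation. Front-loading narrows the spread.

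Nor do the early-occlusion patency curves share the fault to any material degree: at most seven days of immortal time are involved.

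Finally, a Day-90 landmark has limits. It may not support five groups, it drops early abandonments from the display, and it ignores later maintenance procedures. These are real costs, and they favour collapsed groups or a time-dependent count.

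**Conclusion.** The point holds for the curves grouped by procedure count. Following the SAP as written produces a gradient with no true association behind it: about 65% to 95% at 80% patency and 1.5 procedures per person-year, and about 69% to 87% at 2 per person-year with procedures front-loaded. Those sizes rest on assumed rates and 25% dropout. The mechanism itself follows from the plan's definitions. Because confounding by indication opposes it by an unknown amount, neither the direction nor the size of the real slope can be predicted or interpreted. The primary patency estimate is unaffected. The mean-number comparisons in SAP 7.7.4 are a smaller wording point, and the bias in the early-occlusion patency curves is negligible.

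**What to change.** In SAP 7.7.1, for this additional analysis only, choose one of two approaches:

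- Treat the running number of secondary procedures as a time-dependent covariate.
- Use a landmark, for example Day 90. Include subjects whose access is not abandoned and who are still followed, classify them by procedures to date as 0, 1 or 2+, and draw Kaplan-Meier from the landmark to 12 months. List earlier abandonments separately.

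In either case, state that confounding by indication remains and that the result is not an effect of intervening.

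In SAP 7.7.4, report the comparisons by early occlusion and by disruption or pseudoaneurysm as procedures per person-year, the metric that section already uses. The early-occlusion patency curves need at most a Day-7 start.

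Costs: SAP wording and a little code, and fewer procedure groups. With a landmark, early abandonments leave the display and later procedures are not counted. Protocol 13.2.3 and 13.3.3 carry the matching text, so they must be aligned by amendment, or the change noted in the final report as Protocol section 13 provides. SAP 7.9, which now lists no changes to the planned analysis, should record it.

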7.7.2 Secondary Objective #1

Primary Patency through 12 months post AVF creation

Analysis Dataset:

Treated Analysis Set per section **Error! Reference source not found..**

Analysis Method:

Primary patency will be summarized for the Treated population using a Kaplan-Meier curve through at least 12 months. Analyses will include patency/survival probabilities and 95% confidence interval bands through the 12-month visit. The confidence interval will be calculated using a typical transformation of the survival function: $\log(S(t))$. Subjects not completing the study will be censored after their last available patency assessment. A sensitivity analysis shall be performed where a cumulative incidence curve is estimated and death will be accounted for as a competing risk. The cumulative incidence curve will be descriptively compared to $1-S(t)$ where $S(t)$ is the survival function estimated by the Kaplan-Meier method.

The observed cumulative incidence estimate may be calculated using the “cmprsk” library in R, with code similar to the following:

```
cmpout1 <- cuminc(time,event)
```

The event variable is 0 if censored, 1 if an event occurs and 2 if a death occurs. Similar analysis will be conducted on the subcomponents of the endpoint.

Endpoint Definition:

Primary patency is defined as freedom from access thrombosis or any intervention designed to facilitate, maintain or reestablish patency in a thrombosed access from time of access creation. Subsequent to the completion of the AVF creation procedure, consistent with the Training Manual for this staged procedure, the site investigator will assess if an additional PTA balloon maturation or other procedure is needed to promote maturation when outflow is <400 ml/min. Therefore, these specific maturation procedures will not be included in the primary patency endpoint. For time-to-event analysis, day 0 is time of access creation and final date is day of event or day of last follow-up. The definition of primary patency is derived from reporting standards by Sidawy, et al and Shenoy, et al [1,2].

Additional Analysis:

- Primary patency post- surgical or endovascular intervention

7.7.3 Secondary Objective #2

Assisted Primary Patency through 12 months post AVF creation

Analysis Dataset:

Treated Analysis Set per section **Error! Reference source not found..**

Analysis Method:

Assisted primary patency will be summarized for the Treated population using a Kaplan-Meier curve through at least 12 months. Analyses will include patency/survival probabilities and 95% confidence interval bands through the 12-month visit. The confidence interval will be calculated using a typical transformation of the survival function: $\log(S(t))$. Subjects not completing the study will be censored after their last available visit. A sensitivity analysis shall be performed where a cumulative incidence curve is estimated and death will be accounted for as a competing risk. The cumulative incidence curve will be descriptively compared to $1-S(t)$ where $S(t)$ is the survival function estimated by the Kaplan-Meier method.

The observed cumulative incidence estimate may be calculated using the “cmprsk” library in R, with code similar to the following:

```
cmpout1 <- cuminc(time,event)
```

The event variable is 0 if censored, 1 if an event occurs and 2 if a death occurs.

Endpoint Definition:

Assisted primary patency is defined as freedom from access thrombosis from time of access creation. For time-to-event analysis, day 0 is time of access creation and final date is day of event or day of last follow-up. The definition of assisted primary patency is derived from reporting standards by Sidawy, et al and Shenoy, et al [1,2].

Additional Analysis:

- Assisted primary patency post- surgical or endovascular intervention
- Assisted primary patency post- functional cannulation success

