### 5.1 Duration

Once enrolled, subjects shall remain in the study through completion of the required follow-up duration unless the subject withdraws consent, the investigator withdraws the subject, or Medtronic terminates the study for any reason. The enrollment phase is expected to take approximately 13 months. The follow-up duration for each subject is 12 months. The total expected duration of the study is approximately 30 months.

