**Endpoint Definition:**

Cumulative patency is defined as freedom from access abandonment from time of access creation. An abandoned dialysis access is one that can no longer be used for one or two needle prescribed dialysis because it is unable to provide adequate blood flow and/or is deemed unsafe for the patient, and the associated problem cannot be corrected by any intervention either medical, endovascular or surgical.

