4.2.1 Secondary Endpoints

The following secondary endpoints to be evaluated in this study are as follows:

1. Primary patency through 12 months post-AVF creation:

Defined as freedom from access thrombosis or any intervention designed to facilitate, maintain or reestablish patency measured from time of access creation through 12 months.

2. Assisted primary patency through 12 months post-AVF creation:
Defined as freedom from access thrombosis from time of access creation through 12 months.
3. Secondary procedure Rate:
Defined as the percentage of subjects having one or more surgical or percutaneous interventions designed to mature or maintain the AVF or re-establish flow. Secondary procedures are procedures subsequent to completion of the AVF creation procedure. This endpoint will also be summarized by type of procedure, indication, procedure success and association with any adverse events (AEs).
4. Overall patient safety:
A full characterization of all adverse events during the study.

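### Assisted primary patency, and to a lesser extent primary patency, does not count abandonment without thrombosis as a failure, so its curve can sit above one that counts loss of the access

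*SAP*

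**What the plan says.** **Assisted primary patency.** SAP 7.7.3: "Assisted primary patency is defined as freedom from access thrombosis from time of access creation". Protocol 4.1.4 and 13.3.2 and SAP 4.2.1 also name thrombosis as the only failure.

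**Primary patency.** SAP 4.2.1 is broad: "Defined as freedom from access thrombosis or any intervention designed to facilitate, maintain or reestablish patency measured from time of access creation through 12 months". The analysis section, SAP 7.7.2, is narrower: "Primary patency is defined as freedom from access thrombosis or any intervention designed to facilitate, maintain or reestablish patency in a thrombosed access". It then sets aside procedures done to promote maturation when outflow is below 400 ml/min: "these specific maturation procedures will not be included in the primary patency endpoint". Protocol 4.1.4 and 13.3.1 show the same split between broad and narrow wording.

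**Cumulative patency.** Protocol 13.2.3: "Cumulative patency is defined as freedom from access abandonment from time of access creation". An access counts as abandoned when it is "unable to provide adequate blood flow and/or is deemed unsafe for the patient" and the problem cannot be corrected (SAP 7.7.1). Thrombosis is not required. For abandonment due to kidney transplant, SAP 7.7.1 says the "date of censoring is the date their access is abandoned". That rule recurs for functional patency in SAP 7.7.5. It does not appear in SAP 7.7.2 or 7.7.3.

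**Time at risk.** For both secondary endpoints, time runs from access creation to the event or last follow-up. Only subjects who do not complete the study are censored, and death is the only competing event coded.

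**Follow-up.** Protocol 5.1: "Once enrolled, subjects shall remain in the study through completion of the required follow-up duration", with exceptions for withdrawal and study termination. Abandonment is not among the exit reasons in Protocol 9.16.1 or SAP 7.1.1.

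**The concern.** The three patency curves will be read side by side, and a reader will usually take assisted primary patency as a stricter measure than cumulative patency. As written it is not always stricter. An access lost to non-maturation, poor flow or steal, with no thrombosis, is a failure on the primary effectiveness curve and a continuing success on the assisted primary curve.

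These routes to failure are foreseeable from the plan itself. Protocol 10.1 ties the device's clinical risks to achieving maturation and lists arterial steal among the potential events. SAP 10.2 has an end-of-study category for fistulas abandoned before they ever functioned. At stake is the interpretation of a secondary effectiveness curve in a study of newly trained providers.

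**Working it through.** **The plan's own figures.** The documents give no patency, thrombosis or abandonment rate, so there is no stated patency figure to reproduce. The one computed figure, 134 enrolled, reproduces as 100/0.75 = 133.3, rounded up. It is used below only as a denominator.

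**Step 1: follow one subject through the rules.** Take a fistula abandoned for inadequate flow, never thrombosed, with the subject staying in the study.
- Cumulative patency (SAP 7.7.1): failure on the abandonment date.
- Assisted primary patency (SAP 7.7.3): no event, and at risk to last follow-up.
- Primary patency (SAP 7.7.2): no event if no counted intervention came first, for example if only the excluded maturation procedures were done.

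If the subject leaves early, assisted primary patency is censored after the last visit and primary patency at the last patency assessment. That censoring is informative, and still not a failure.

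**Step 2: counting identity, no censoring.** Among N treated subjects let a = abandoned without thrombosis, b = thrombosed and then abandoned, c = thrombosed and salvaged. Assume no abandoned fistula has a thrombosis recorded later.
- Cumulative = 1 − (a + b)/N
- Assisted as written = 1 − (b + c)/N
- Assisted with abandonment counted = 1 − (a + b + c)/N

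The last two differ by exactly a/N. Assisted as written exceeds cumulative when a > c. With abandonment counted, assisted can never exceed cumulative.

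**Step 3: illustrations (all rates assumed).**

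| Abandoned, no thrombosis | Thrombosed | Salvaged share | Cumulative | Assisted as written | Assisted, abandonment counted |
|---|---|---|---|---|---|
| 10% | 12% | 50% | 1 − 0.10 − 0.06 = 84% | 88% | 78% |
| 15% | 12% | 50% | 1 − 0.15 − 0.06 = 79% | 88% | 73% |
| 5% | 15% | 20% | 1 − 0.05 − 0.12 = 83% | 85% | 80% |
| 5% | 15% | 50% | 1 − 0.05 − 0.075 = 87.5% | 85% | 80% |

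The first three rows have a > c and the order reverses. In the fourth, 5% is below 7.5% and it does not, yet assisted as written is still 5 points above the version that counts abandonment.

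On the scale of N = 134:
- a = 10, b = 5, c = 5: assisted 124/134 = 92.5%, cumulative 119/134 = 88.8%, assisted with abandonment counted 114/134 = 85.1%.
- a = 5, b = 5, c = 10: assisted 119/134 = 88.8%, cumulative 124/134 = 92.5%, so no reversal.

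**Step 4: with censoring.** A large-sample Kaplan-Meier simulation used exponential times and 25% dropout by day 360. With 10% non-thrombotic abandonment and 10% thrombosis, half salvaged, it gave assisted as written 90.5%, cumulative 85.5% and assisted with abandonment counted 81.0%. The gap is 9.5 points against a nominal 10%. With 20% abandonment the figures were 91.0%, 76.0% and 72.0%, a gap of 19 points. Censoring at abandonment instead does not help: in the 10%/10% case assisted is 90.0%, still above 85.5%.

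**The case against.** **The endpoints measure different things.** A low-flow fistula that is abandoned but not clotted is truthfully free from thrombosis, and nothing in the documents promises that the three curves are nested. This is fair: the curve is not wrong as a thrombosis-free curve. The trouble is that it is labelled and reported as patency, beside a curve on which the same access has failed.

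**The failures are reported elsewhere.** A reader might infer that non-thrombotic failures are concealed. The documents do not support that. They are events in the primary effectiveness endpoint and in functional patency, and SAP 10.2 tabulates abandonment as an end-of-study status. Physiological maturation and functional cannulation also bear on non-maturation.

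**Unseen sources.** SAP 7.7.2 and 7.7.3 say their definitions derive from two cited reporting standards. The clinical events committee charter and the endpoint mapping file (SAP 10.1) may hold operating rules. Thrombosis has no operational definition in either document. A reader might infer that a deliberately ligated access is scored as patent, but that cannot be shown, because a closed access with no flow might be adjudicated as thrombosis. An access with flow that is abandoned as inadequate or unsafe does not depend on that question.

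**Reversal is not certain.** A reader might infer that assisted primary patency will exceed cumulative patency. It will do so only if non-thrombotic abandonments outnumber salvaged thromboses, and the documents give no rates from which to judge that.

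**Primary patency is partly protected.** A counted intervention may often precede abandonment, since abandonment requires a problem that cannot be corrected. This stands. The exposure is larger under the narrow wording of SAP 7.7.2 than under SAP 4.2.1, and no figure can be put on it.

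**Low stakes.** These are descriptive secondary endpoints with no hypothesis test. That limits the severity but does not remove the gap.

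**Conclusion.** The point holds on the stated rules. An access abandoned without thrombosis fails cumulative patency but is never a failure of assisted primary patency. The assisted curve is therefore higher than one that counts loss of the access, by about the share abandoned without thrombosis. That equality is exact only without censoring and if no abandoned fistula is later recorded as thrombosed. Under the assumed rates the difference is 5 to 15 points in the tabulated cases. Reversal of the order against cumulative patency is possible, not certain. Primary patency shares the gap only where neither a counted intervention nor a thrombosis comes before abandonment. The primary effectiveness endpoint is unaffected. The change is worth making, but the matter concerns how secondary curves are read and not the study's main conclusion.

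**What to change.** In Protocol 4.1.4, 13.3.1 and 13.3.2 and SAP 4.2.1, 7.7.2 and 7.7.3:

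1. Count access abandonment, as defined in SAP 7.7.1, as a failure event for assisted primary patency and for primary patency.
2. Copy into SAP 7.7.2 and 7.7.3 the SAP 7.7.1 rule that abandonment due to kidney transplant is censored at the abandonment date. Neither section has it now, so it must be added.
3. Keep the thrombosis-only curve as a supplementary analysis, so that the definition the SAP derives from its cited standards is still reported.

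Abandonment dates are already needed for cumulative patency, so no new data are required. The costs are slightly less favourable secondary patency figures and an amendment to both documents, with the approvals described in Protocol 14.1 and 15.6.
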